7. PHARMACODYNAMIC ANALYSES

7.1. Primary Pharmacodynamics Analyses

The three PET scans per subject will be denoted as 'Pre-dose' (Baseline PET in Period 2), 'PET1' (Period 2, Day 1, 30 minutes PET after dose of GSK3008348, allowable time window is 20-60 mins) and 'PET2' (Period 2, Day 2, 24 hours PET after dose of GSK3008348, allowable time window is 14-28 hrs).

7.1.1. Endpoint / Variables

Change in the uptake of [¹⁸F]-FBA-A20FMDV2 in the whole lung (assessed as the volume of distribution [V_T], not corrected for air volume) at approximately 30 min post-dose compared to pre-dose, as measured by PET. V_T is implicitly corrected for blood volume.

7.1.2. Summary Measure

Ratio (PET1/Pre-dose) in the volume of distribution (V_T), not corrected for air volume at approximately 30 min post-dose as measured by PET.

7.1.3. Population of Interest

The primary pharmacodynamic analyses will be based on the Per-Protocol (PP) population, unless otherwise specified.

7.1.4. Strategy for Intercurrent (Post-Randomisation) Events

Several post-randomisations events have been considered e.g. use of rescue medication, discontinuation of treatment, treatment switching and death. Due to the short duration of the study (and the time at which the pharmacodynamic endpoint is measured; baseline, 30mins and 14-28hrs post-dose) these post-randomisation events have been deemed to have little impact on the endpoint.

Therefore, a treatment policy approach will be adopted hence the actual values of the endpoint regardless of whether the intercurrent event has occurred will be analysed.

7.1.5. Statistical Analyses / Methods

Details of the planned displays are provided in Appendix 12: List of Data Displays and will be based on GSK data standards and statistical principles.

Unless otherwise specified, endpoints/variables defined in Section 7.1.1 will be summarised using descriptive statistics, graphically presented (where appropriate) and listed.

7.1.5.1. Statistical Methodology Specification

Endpoint / Variables

V_T (whole lung, not corrected for air volume), at 1000 mcg GSK3008348

Timepoint

• The primary timepoint of interest is the 30 minutes post-dose PET scan timepoint.

Model Specification

- The distribution of V_T will be explored using graphical approaches. It is likely that this follows a log-normal distribution in which case the logarithm transformation will be applied, and a normal distribution assumed for log (V_T).
- Only data from those subjects receiving 1,000 mcg GSK3008348 will be included in the primary analysis (i.e., no placebo data will be included) in Cohort 1.
- The three PET scans per subject will be denoted by Pre-dose (Baseline PET in Period 2), PET1 (Period 2, Day 1, 30 minutes PET after dose of GSK3008348, allowable time window is 20-60 mins) and PET2 (Period 2, Day 2, 24 hours PET after dose of GSK3008348, allowable time window is 14-28 hrs).
- The mean of the normal distribution will be allowed to vary per post-dose scan timepoint by defining the 3-dimensional array parameter ResponsebyVisit as follows:
 - o ResponsebyVisit[1] = mean of log (Response) at 'Pre-dose'
 - ResponsebyVisit[2] = mean of log (Response) at 'PET1'
 - ResponsebyVisit[3] = mean of log (Response) at 'PET2'
- In addition, the following 3 dimensional array parameter ResponseRatio will also be created:
 - o ResponseRatio[1] = PET1/Pre-dose
 - o ResponseRatio[2] = PET2/Pre-dose
 - o ResponseRatio[3] = PET2/PET1
- The inclusion of covariates Age, Sex, Baseline % predicted FVC, and Baseline % predicted DLCO (baseline from Period 2) will be explored in a sequential manner and included in the model if the 95% HPD credible interval for the corresponding regression coefficient excludes 0.
- This endpoint will be analysed using Bayesian inference assuming non-informative priors of the form N(mean=0, SD = 1000) for all regression coefficients in the model.
- An unstructured 3x3 variance-covariance matrix will be assumed to model the
 dependency between log (V_T) in the three PET scans. If the model fails to converge
 then additional structures such as the Toeplitz structure should be explored. Details
 of the prior distributions are presented in Section 12.2.

Model Checking & Diagnostics

• Refer to Section 12.2: Model Checking and Diagnostics for Statistical Analyses.

Model Results Presentation

- Plots of the posterior samples (chains) will be produced for all the parameters in the model as listings.
- Posterior density plots for V_TRatio;

- o PET1/Pre-dose
- o PET2/Pre-dose
- o PET2/PET1

will be produced.

- The adjusted posterior median values of V_TRatio (PET1/Pre-dose, PET2/Pre-dose and PET2/PET1) will be presented in tabular form together with the corresponding standard deviations and 95% HPD credible intervals.
- Plots of individual subject data for PET1/Pre-dose, PET2/ Pre-dose and PET2/PET1 will be superimposed with the adjusted posterior median values of PET1/Pre-dose, PET2/Pre-dose and PET2/PET1 respectively. These plots should also include the corresponding 95% HPD credible intervals for PET1/Pre-dose, PET2/Pre-dose and PET2/PET1.
- The posterior probability that the true ratio PET1/Pre-dose is less than 1 will be calculated.

Subgroup Analyses

None

Sensitivity and Supportive Analyses

• Following review of the data, additional analyses may be conducted to further support the primary statistical analysis, if deemed appropriate. The posterior probability that the true ratio PET1/Pre-dose is less than 0.9, 0.8, 0.7 and 0.6, as appropriate depending on the observed data, will also be calculated. If the PP and ITT populations differ, the same statistical analysis using the ITT population will also be conducted.

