## 5.4. Scientific Rationale for Study Design

- Cohort 1 includes a placebo control to allow assessment of safety and tolerability, as reporting of adverse events in patients receiving placebo will facilitate the differentiation between ‘disease’ and ‘intervention’ adverse events.
- Cohort 1 will be conducted in a double-blind (sponsor unblind) fashion. Safety and PK data reviews will be conducted without treatment group assignment or subject numbers, so that the investigators and data review team remain blinded. The

statistician will perform an unblinded review of PET data as part of the pre-planned interim analysis, to allow appropriate decision-making. The sponsor (including the medical monitor) may also undertake separate in-stream review of unblinded data to help determine the most appropriate response to emerging data.

- The number of patients to be enrolled in Cohort 1 (7 participants) is based on the probability of detecting a change in  $\alpha\beta 6$  internalisation at approximately 30 min post-dose compared to pre-dose of 6% or greater, as measured by the uptake of [F]-FBA-A20FMDV2 in the lungs reported as the volume of distribution [VT]. This predetermined change is equivalent to approximately half the difference in [F]-FBA-A20FMDV2 PET signal observed between healthy volunteers and IPF patients in a previous study RES116235. If GSK3008348 cannot achieve that reduction in  $\alpha\beta 6$ -associated PET signal and the endpoint variability is as expected, then the study will end.
- The design for Cohort 2 will be defined following completion of Cohort 1, to ensure the most informative doses of GSK3008348 are selected and the PET scans are timed appropriately. Cohort 2 data may be reviewed in-stream and the design of Cohort 2 adjusted to maximise the value of the data obtained. The aim is to assess target engagement while exposing the smallest possible number of patients to ionising radiation from the PET procedure.

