# **10. STATISTICAL CONSIDERATIONS**

## **10.1. Sample Size Determination**

This study is designed to assess the level of receptor engagement as measured by the effect of nebulised GSK3008348 on the  $\alpha\beta6$ -associated PET signal ( $V_T$ ). The PET data from the 5 participants in Cohort 1 receiving GSK3008348 will be used. This sample size has been chosen based on considerations given to: a) the probability of declaring a successful study for reductions in  $\alpha\beta6$ -associated PET signal deemed to be representative of the expected receptor engagement activity, and b) the within-subject variability of the PET signal.

The chosen study success criteria is defined as  $\text{Prob}(\theta < 0 | \text{Study Data, Prior}(\theta)) \geq 80\%$ , where  $\theta$  is the unknown true logarithm of the ratio of  $\alpha\beta6$ -associated PET signal post-dose / pre-dose in patients receiving GSK3008348, and the prior distribution for  $\theta$  is non-informative. Assuming the within-subject standard deviation is as previously observed in study [RES116235](#) (within-subject standard deviation following two PET scans was estimated to be 0.15, 95% CI [0.099, 0.34]), consideration was given to the probability of achieving the study success criteria for a range of true reductions in  $\alpha\beta6$ -associated PET signal with GSK3008348. In addition, the minimum detectable effect (MDE), i.e., the minimum observed reduction in  $\alpha\beta6$ -associated PET signal leading to the success

criteria being achieved, was also derived. In particular, if the true reduction in  $\alpha\beta 6$ -associated PET signal is 14% then there is 86% probability of achieving the above success criteria, and the MDE is a 6.2% reduction in  $\alpha\beta 6$ -associated PET signal.

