5. CONSIDERATIONS FOR DATA ANALYSES AND DATA HANDLING CONVENTIONS

5.1. Study Treatment & Sub-group Display Descriptors

Treatmo	Treatment Group Descriptions					
RandAll NG Data Displays for Reporting						
Code	Description	Description	Order in TLF			
A	Placebo	Placebo	1			
В	GSK3008348 1000 mcg	GSK3008348 1000 mcg	2			

No treatment comparisons between GSK3008348 1000 mcg versus Placebo will be conducted.

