7.2. Secondary Pharmacodynamic Analyses

The secondary pharmacodynamic analyses will be conducted in the same manner as the primary pharmacodynamic analyses. The only difference is that the timepoint of interest is now PET2. The output corresponding to the secondary pharmacodynamic analysis will be obtained from the primary pharmacodynamic analysis and corresponds to PET2/Predose and PET2/PET1.

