12.1.5.2. Table Illustrating Study Decision Making Used at Interim Analysis

	Interim outcomes from	Impact on development of				Cohort 2 -	Cohort- 2
	204715	GSK3008348	Traffic lights	Question for cohort 2	Cohort 2	Positive data	negative data
	No signal, variability as						
1)	expected	Stop development					
	Signal more variable than	Failure of PET					
	expected, sample size	endpoint not '348					
	increase required >10	continue to PD					
2)	subjects	study (pSMAD2)		N/A			
		Dependent on					
		number					
		additional					
		subjects required.					
		If the number of					
		patients can be					
		feasibly recruited,					
		continue to cohort					
		2 to get definitive			If Answer to		
		answer. If it is			both questions		
		not feasible to			yes, recruit		
		increase the			additional		
		sample size-		Can target engagement	subjects and		
		failure in		be established in the	confirm target		Still no robust
	Signal more variable than	sensitivity of PET		larger cohort? Is this	engagement.		target
	expected, sample size	endpoint continue		only 10 or less	Otherwise	1) invest API-3	engagement-
	increase required <10	to PD study		subjects and can these	continue to PD	and repeat dose	Stop
3)	subjects	(pSMAD2)		be feasibly recruited?	study	IPF study	development
				Is GSK3008348			
				suitable for twice daily			
		Go ahead with		dosing? Can this be			
	Signal at 30 minutes, but no	API-3 and repeat		achieved in a number			
	or inconclusive signal at 24	dosing studies in		of participants that can			
4)	hours (expected outcome)	IPF patients		be feasibly recruited?			

[figure not shown]
CONFIDENTIAL

	Interim outcomes from 204715	Impact on development of GSK3008348	Traffic lights	Question for cohort 2	Cohort 2	Cohort 2 - Positive data	Cohort- 2 negative data
							Use
		Go ahead with				Use information to	information to
		API-3 and repeat				inform dose	inform dose
		dose study with		Investigate whether		selection for	selection for
	Signal at both 30 mins and	PD assessments		lower doses can be	Investigate	repeat dosing in	repeat dosing
5)	24 hours	in IPF patients		used?	lower doses	IPF study	in IPF study

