12.1.5.4. Figure Illustrating Study Decision Making Used at Interim Analysis

12.2. Model Checking and Diagnostics for Statistical Analyses

12.2.1. General Considerations for Bayesian Analysis

- The following points are for guidance and illustration only and do not guarantee a successful model convergence. They cannot cover all eventualities and do not remove the requirement to do what is best for the specific set of observed data being modelled.
- Unless otherwise stated, data collected at screening and at unscheduled time points will not be included in the statistical analyses, i.e., only planned/scheduled post-screening data will be included except where screening data is used as baseline.
- All credible intervals reported will be 95% HPD intervals, unless otherwise specified.
- After Markov Chain Monte Carlo (MCMC) for Bayesian inference, estimated and monitored model parameters (variance components and fixed effects) were compared to corresponding estimated parameters from the linear mixed model. Confidence was gained if results were similar. Different initial values for fixed effects (but not

variance components) were used to assess convergence. Convergence for all the parameters in the model needs to be verified

• A separate seed for each MCMC chain will be set to ensure reproducibility.

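### Does the active-only PET1/Pre-dose analysis need an active-versus-placebo contrast to support attribution to GSK3008348?

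*SAP*

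**What the plan says.** The primary model takes the 1,000 mcg arm alone: "Only data from those subjects receiving 1,000 mcg GSK3008348 will be included in the primary analysis (i.e., no placebo data will be included" (SAP Section 7.1.5.1). The secondary result comes from the same fit and "corresponds to PET2/Predose and PET2/PET1" (SAP Section 7.2). The exploratory and interim models follow it. SAP Section 5.1 adds that "No treatment comparisons between GSK3008348 1000 mcg versus Placebo will be conducted", and Section 5.5 repeats this.

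The protocol takes the same line. Section 10.1 sizes the study on the active arm: "The PET data from the 5 participants in Cohort 1 receiving GSK3008348 will be used". Sections 10.1 and 10.3.5.1 define the log ratio only for patients given the drug. Section 5.4 gives the reason for the control arm: "Cohort 1 includes a placebo control to allow assessment of safety and tolerability". The endpoint in Section 4 is worded as a change against pre-dose.

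The two placebo participants are scanned too, because protocol Section 5.1.1 completes Cohort 1 only when all 7 have a 30-minute scan. Their points appear in SAP Figures 3.1 to 3.8 and in the PET listings. Tables 3.3, 3.4, 3.7 and 3.8 exclude them. Tables 3.1, 3.2, 3.5 and 3.6 carry no such exclusion.

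**The concern.** Scan order is fixed, and the pre-dose scan may precede PET1 by up to 14 days. The analysis therefore asks whether V_T fell between scan 1 and scan 2, not whether the drug made it fall. The protocol's standard deviation describes random scan-to-scan variation, and neither document gives a mean test-retest change. Protocol Section 3.3.1 names one non-drug route to a lower signal, antibodies against the tracer, although it rates that risk low and reports no signal loss so far.

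SAP Section 3.1 records that the study stopped for success on this within-arm change. Randomised placebo participants have the same scans, yet no between-arm estimate is planned, so a reader sees placebo points next to an active estimate with no interval for the difference. If a modest drift existed, it could pass for receptor engagement.

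A smaller related point is that protocol Appendix 9 expects antibody results to be related to imaging observations, while the SAP lists the two separately.

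**Working it through.** **Inputs.** There are 5 active and 2 placebo participants. Success is a posterior probability of at least 80% that the log ratio is below 0. The variability is from protocol Section 10.1: "within-subject standard deviation following two PET scans was estimated to be 0.15, 95% CI [0.099, 0.34". I carry two readings: 0.15 as the SD of the log ratio, and 0.15 per scan, which gives a log-ratio SD of 0.15 x sqrt(2) = 0.212. Results below are in that order. Drift sizes are assumptions.

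**The plan's own figures.** With a flat prior, success requires a mean fall above t(0.80, 4 df) x SD/sqrt(5).
- SD 0.15: SE = 0.15/sqrt(5) = 0.0671. The minimum detectable effect is 1 - exp(-0.941 x 0.0671) = 6.1%, against 6.2% stated. At a 14% reduction the noncentral t gives 90.3%. Averaging over uncertainty in the SD (6 to 7 df, matched to the stated interval) gives 84.9-85.7%, against 86% stated.
- SD 0.212: 8.5% and 74.9%, which does not reproduce the protocol. The first reading is therefore the better supported.

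**False success from drift, no drug effect.** P = 1 - F(0.941; 4 df, noncentrality -ln(r)/SE), where F is the noncentral t distribution function and r is the non-drug ratio.

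| Prior | No drift | 5% fall | 10% fall |
|---|---|---|---|
| Flat | 20% / 20% | 46% / 37% | 74% / 59% |
| Inverse-Wishart(3, 0.02 x identity), a rescaled example | 17% / 20% | 42% / 37% | 72% / 59% |
| Inverse-Wishart(3, identity), the default in SAP Section 12.2.1.1 | 0.004% / 0.2% | 0.07% / 1.0% | 0.8% / 4% |

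Under the default prior the log ratio has a t posterior with 5 df and scale sqrt((2 + SS)/25). With SS = 4 x 0.15^2 = 0.09 the scale is 0.289, so success needs an observed fall of about 1 - exp(-0.920 x 0.289) = 23%. The SAP allows rescaling and does not say which prior the interim used.

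**What a ratio of ratios would give.** With a flat prior, SE = SD x sqrt(1/5 + 1/2) = 0.1255 / 0.1775 on 5 df.
- 95% limits: exp(2.571 x SE) = a factor 1.38 / 1.58 either way. Under the default prior the factor is about 3.4 / 3.5.
- Chance that the interval excludes 1 at a true 14% reduction (-ln 0.86 = 0.1508): 1 - F(2.571; 5 df, 0.1508/SE) = 0.16 / 0.10.
- Placebo ratio alone, using the pooled SD: SE = SD/sqrt(2) = 0.106 / 0.150, limits a factor 1.31 / 1.47. A true 10% placebo fall would be detected with probability 0.13 / 0.08.

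**The check already in the plan.** The expected interim outcome in SAP Section 12.1.5.2 is a 30-minute signal with no "or inconclusive signal at 24" hours. Recovery at PET2 argues against a persistent drift. Full recovery from a 14% fall is a ratio of 1/0.86 = 1.16. With 5 active participants the 95% limits on PET2/PET1 are a factor exp(2.776 x SE) = 1.20 / 1.30, and the interval excludes 1 with probability 0.40 / 0.23. By the study's own 80% rule, recovery would be declared with probability 0.90 / 0.75. On either standard PET2 tells more than the placebo contrast would.

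**The case for a change.** The strongest case for a change is that the scans exist and the radiation has been given. The extra fit is also cheap: SAP Section 12.2.1 already runs a comparison model, since Bayesian estimates "were compared to corresponding estimated parameters from the linear mixed model". A labelled descriptive contrast would put an interval where readers otherwise compare points by eye. SAP Section 7.1.5.1 allows additional supportive analyses only in general terms, while Sections 5.1 and 5.5 rule out this one.

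Part of this stands. The between-arm contrast is absent, and PET2 is only a partial check, because it fails if engagement lasts to 24 hours or if the drift is transient. The false-success figures under a flat or rescaled prior are not small.

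The rest does not carry. An interval of a factor 1.38-1.58 cannot speak to a 5-10% drift in either direction. With two placebo participants the individual ratios are all the information there is, and Figure 3.2 appears to plot them already. SAP Sections 7.1.2, 7.1.3 and 7.1.5, with Tables 3.1, 3.2, 3.5 and 3.6, may also summarise placebo ratios descriptively, although the table shells are not available to confirm it. The contrast would be a comparison added after the interim that the plan deliberately excludes, and it could not alter a decision already taken.

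On antibodies, Listings 29, 34 and 35 hold both sets of results by participant. In a cohort of this size, a combined listing would only re-tabulate them.

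**Conclusion.** No change to the plan is needed. The active-only analysis is a design choice shared by protocol and SAP, the endpoint is already a change from baseline, and no document reports a drift. The possible inflation of false success (from 20% to 37-46% at a 5% fall and 59-74% at 10%, flat prior) rests on assumed drifts. It drops to at most about 4% under the SAP's default covariance prior. The placebo contrast would not resolve it, since it has a 0.16 / 0.10 chance of excluding 1 at the design effect and cannot exclude a 5-10% drift.

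These figures assume log-normal V_T, equal variance in both arms and all 7 participants evaluable. The point that remains is one of interpretation: attributing the PET1/Pre-dose change to GSK3008348 assumes negligible non-drug change between scans. A careful report would say so next to the individual placebo ratios, within the plan as written.

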12.2.1.1. Prior Distributions

Unless otherwise specified, the following will be the default approach to selecting prior distributions:

- Non-informative priors of the form Normal (0, Var=1E6) will be assigned to each fixed-effect parameter in the proposed statistical model.
- For repeated measures models, non-informative Inverse-Wishart priors of the form IW (υ, Σ) will be assigned for the Variance-Covariance (VC) matrix associated with the repeated measures timepoints. The parameter υ represents the dimension of VC (number of rows or columns) and the matrix Σ is an identity matrix of the same dimension as VC. The unstructured variance covariance structure for the repeated measurements will be assumed. In cases of non-convergence, the Toeplitz structure will be used.
 - o If there are issues with these distribution parameters, then Σ may be a diagonal matrix that uses best guesses for the residual variance at each repeated measure timepoint (or the residual estimate from fitting simple models). This only needs to be of the correct order of magnitude.
- Non-informative inverse-gamma priors of the form IG(a=2.001, b=0.001) will be used for scale parameters (variances). If these parameters do not lead to convergence, then choose "a" small and "b" smaller than the expected standard deviation.

It is good practice to ensure that each prior distribution is visualized to ensure it appears sensible, i.e., that it allows parameter values that generate clinically plausible response values and that it is truly non-informative over the region of the likelihood function where the data lies.

Note:

• The Gamma(a,b) density function takes the form

$$p(u) = \frac{b(bu)^{a-1}e^{-bu}}{\Gamma(a)}, u > 0$$

The mean is a/b and the variance is a/b^2 .

• The IG(a,b) density function takes the form

$$p(u) = \frac{b^a u^{-(a+1)} e^{-b/u}}{\Gamma(a)}, u > 0$$

The mode is b/(a+1), the mean is b/(a-1), if a>1, and the variance is $b^2/[(a-1)^2(a-2)]$, if a>2.

• There is no requirement to formally report the prior visualisation outputs.

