12.2.1.3. Convergence Diagnostics

To be able to perform Bayesian inference using MCMC simulations the posterior samples for all the parameters in the model need to be obtained from the corresponding target posterior distribution. To ensure that this is the case the following is a list of convergence diagnostics that can be applied for each parameter:

Comparing MCSE vs. posterior standard deviation:

- The Monte Carlo Standard Errors (MCSE) should be compared with the standard deviation of the posterior distribution (SD) to ensure that only a fraction of the posterior variability is due to the simulation, i.e., the ratio MCSE/SD should be as small as possible, typically < 0.01.
- Adequate values for the number of MCMC samples / thinning / number of burn-in samples should be chosen to ensure that the ratio MCSE/SD for all the parameters in the model is < 0.01.
- In addition, if possible, the number of tuning units and maximum number of tuning iterations may be increased to find a better proposal distribution for the model parameters, which in turn may reduce the MCSE/SD ratio.
- Where possible the code should be written to allow the SAS compiler to identify and make use of conjugacy, since this can greatly reduce the corresponding MCSE/SD ratio.
- Models selected with MCSE/SD values > 0.01 would need a brief remark/justification added to the CSR to clarify why it was not possible to reach the target and why it is believed the subsequent model still has utility from an inference perspective.

Gelman & Rubin diagnostics:

- The Gelman & Rubin diagnostic assessment will be used to assess convergence of the multiple chains.
- The Gelman & Rubin diagnostic is based on running multiple Markov chains, say m, each with n draws, with the different chains started at initial values that should be overdispersed relative to the target posterior distribution. Thus, the m chains yield m possible inferences; to answer the question of whether these inferences are similar enough to indicate approximate convergence, Gelman, 1992 suggested comparing these to the inference made by mixing together the m*n draws from all the sequences as follows: the pooled variance across the chains is compared to the overall within-chain variance using a ratio, usually called the potential scale reduction factor, or \hat{R} .
- Values of \hat{R} close to 1 indicate that each of the m sets of n simulated observations is close to the target posterior distribution.

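### The posterior SD tabulated beside the median V_T ratio has no usable value on the ratio scale under the SAP's default prior; give it on the log scale or drop it

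*SAP*

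**What the plan says.** SAP 7.1.5.1 (Model Results Presentation) tabulates adjusted posterior medians of the three V_T ratios, PET1/Pre-dose, PET2/Pre-dose and PET2/PET1, "together with the corresponding standard deviations and 95% HPD credible intervals". As worded, the SD belongs to the ratio. Nothing puts it on the log scale, and the table shells are not in the document (SAP Appendix 13).

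The model behind the table is set out in three places:

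- **Data.** Protocol 10.1: "The PET data from the 5 participants in Cohort 1 receiving GSK3008348 will be used". SAP 7.1.5.1 confirms that "no placebo data will be included" in the primary analysis.
- **Likelihood and means.** SAP 7.1.5.1 expects to model log V_T as normal, with a mean for each scan and N(0, SD 1000) priors. "An unstructured 3x3 variance-covariance matrix will be assumed".
- **Covariance prior.** SAP 12.2.1.1 uses an inverse-Wishart whose degrees of freedom equal the dimension, here 3, and "the matrix Σ is an identity matrix of the same dimension as VC". If this causes difficulty, a diagonal scale built from best-guess residual variances may replace it.

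SAP 12.2.1 sets a seed for each chain. SAP 12.2.1.3 asks for enough sampling that "the ratio MCSE/SD for all the parameters in the model is < 0.01". The number of draws is not stated. SAP 7.2 and 7.3 carry the same approach to the secondary and exploratory ratios.

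**The concern.** The model works on the log scale, and the ratio is the exponential of a difference of log means. With five participants and an unknown covariance, that difference has heavy Student t tails. Medians, HPD intervals and tail probabilities cope with this. An SD taken on the ratio scale does not: exponentiation turns the heavy upper tail into rare, enormous draws, and their squares dominate the sum.

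At stake is one descriptive column. A reader could naturally take it as the precision of the estimated ratio, for instance when planning a later PET study, although the figure mostly reflects the seed and the run length.

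**Working it through.** **Inputs.** n = 5 and within-subject SD 0.15 (Protocol 10.1); 3 scans, inverse-Wishart with 3 df and identity scale, and means N(0, SD 1000) (SAP 7.1.5.1 and 12.2.1.1). Assumptions: an observed 14% reduction (the Protocol 10.1 planning value), 10,000 to 1,000,000 draws, and a between-subject log SD of 0.3 in the constructed dataset.

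**Step 1. The plan's own figures.** The documents give no value for the SD of the ratio, so only the planning figures can be checked. Reading 0.15 as the SD of the paired log difference, the minimum detectable effect is 1 − exp(−0.941 × 0.15/√5) = 6.1%, against 6.2% stated. The probability of success is 90.3% with the SD fixed, 87.4% if 14% is entered as 0.14 on the log scale, and 84.8% to 85.5% averaged over uncertainty in the SD (6 to 7 df assumed); 86% is stated. Reading 0.15 as a per-scan SD gives a paired SD of 0.15 × √2 = 0.212, hence 75% and 8.5%, which do not match. Both readings are carried forward because the conclusion is the same.

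**Step 2. Posterior of the log ratio.** With effectively flat means, the visit means are multivariate t with df = 3 + (5 − 1) − 3 + 1 = 5 and scale matrix (I + S)/(5 × 5), where S is the sum-of-squares matrix. For PET1 minus Pre-dose, the identity contributes 1 + 1 = 2 and the data contribute 4 × SD²:

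- Paired SD 0.15: scale = √((2 + 0.09)/25) = 0.289; log-scale SD = 0.289 × √(5/3) = 0.373.
- Paired SD 0.212: scale = √((2 + 0.18)/25) = 0.295; log-scale SD = 0.295 × √(5/3) = 0.381.

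**Step 3. Moments of the ratio.** The exponential of a t variable has no finite mean or variance. The N(0, SD 1000) priors eventually cut the tail. The prior variance of a difference is 2 × 10⁶, so the formal SD is of order exp(2 × 10⁶), about 10^868,589. It is finite, but no run can approach it.

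**Step 4. Effect of the seed.** A Gibbs sampler of the SAP model on one constructed dataset (14% reduction, per-scan SD 0.15), 12 seeds of 50,000 draws:

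| Summary | Range over 12 seeds |
|---|---|
| SD of ratio | 0.437 to 4.23 |
| SD of log ratio | 0.377 to 0.390 |
| Median ratio | 0.858 to 0.862 |
| 95% HPD, lower limit | 0.30 to 0.32 |
| 95% HPD, upper limit | 1.62 to 1.65 |
| P(ratio < 1) | 0.678 to 0.686 |

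In the seed that gave 4.23 the largest draw was 932. That draw alone contributes about 931²/50,000 = 17.3 to a variance of 4.23² = 17.9. A second check, 8 seeds of 50,000 draws on one fixed dataset, gave ratio SDs of 0.47 to 16.2 with log-scale SDs of 0.371 to 0.377.

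**Step 5. Effect of run length.** Direct draws at scale 0.295, SD of the ratio over repeats:

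| Draws | 5th percentile | Median | 95th percentile |
|---|---|---|---|
| 10,000 | 0.405 | 0.468 | 1.83 |
| 100,000 | 0.456 | 0.623 | 8.4 |
| 1,000,000 | 0.69 | 2.95 | 189 |

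The figure climbs with sampling instead of settling.

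**Step 6. Would the convergence check show it?** MCSE is essentially SD/√ESS, where ESS is the effective sample size. MCSE/SD is therefore 1/√ESS, and the 0.01 limit asks for an ESS of about 10,000. The SD cancels, so the check can pass while the SD is arbitrary.

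**Step 7. Other priors.** With the fallback scale (assumed diagonal 0.0225) and paired SD 0.212, the t scale is √((0.045 + 0.18)/25) = 0.095. At 100,000 draws the ratio SD has 5th, 50th and 95th percentiles 0.107, 0.109 and 0.118, maximum 0.237. A flat-prior paired analysis (4 df), which is not the SAP's model, gives 0.083, 0.085 and 0.109 at paired SD 0.15, and 0.120, 0.126 and 0.267 at 0.212.

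**The case against.** The best defence is that this column decides nothing. The success rule is a posterior probability, the same table gives the median and HPD interval, and SAP 12.2.1 makes 95% HPD the standard interval. No section uses the SD as an error bar. All of that stands and keeps the point small.

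The large spread also comes mainly from the identity scale, which adds 2 to a data sum of squares of only 0.09 to 0.18. SAP 12.2.1.1 allows a smaller scale and recommends looking at each prior. That stands too, but the fallback is optional and identity is the stated default.

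The intended scale is inferred, since the shells are not available. If they already show a log-scale SD, a label is enough.

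Three stronger readings are tempting, and the documents do not support them:

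- **That the SD is infinite.** The proper priors on the means make it finite, though useless.
- **That the printed value cannot be reproduced.** The fixed seeds make a given run repeatable. They do not make the SD meaningful, because another seed or run length gives another value.
- **That the SD corrupts the MCSE/SD check.** It cancels from that ratio; the check simply does not see the problem.

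**Conclusion.** The point holds as a minor reporting fault. Under the default prior, with the SD read on the ratio scale, the tabulated figure is not a usable measure of uncertainty: at 50,000 draws it ran from about 0.4 to above 4 on identical data, and to 16 in a second check, and it grows with longer runs. The log-scale SD, about 0.37 to 0.39 on the same model, is stable.

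This rests on five active participants with complete scans, the identity-scale inverse-Wishart, an observed reduction of about 14%, and an assumed number of draws. Under the fallback scale the instability is mild at ordinary run lengths, and under a flat prior it is usually mild.

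A reader might infer that the interim success decision is in doubt. This point gives no ground for that: P(ratio < 1) is stable across seeds, and the SD does not enter the rule. Whether the identity scale suits that probability is a separate question about the prior.

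**What to change.** In Tables 3.3, 3.4, 3.7 and 3.8, replace the SD of the ratio with the posterior SD of the log ratio and label it so, or remove the column. Keep the median ratio, the 95% HPD interval and the posterior probability. One sentence in SAP 7.1.5.1 should state the scale; SAP 7.2 and 7.3 inherit it. Applying the MCSE/SD limit to the log-scale means and contrasts would also be sensible.

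The cost is one column in four tables. It needs no new data or refitting, since the log-ratio draws are the logs of those already produced, and no conclusion changes. SAP 1.1 places the amendment before the final database freeze, so the final tables could take the change; Table 3.3 was also an interim output, and any SD shown there should carry a note.
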